4. RESEARCH QUESTIONS AND OBJECTIVES

The primary study objective is to evaluate the impact of the risk minimization measures on HCP and patient understanding regarding the risk of hypoglycemia and/or hyperglycemia due to medication errors associated with administration of Humalog U-200 KwikPen as communicated through the risk minimization measures.

The secondary objective is to evaluate behavior of HCPs and patients regarding the risk of hypoglycemia and/or hyperglycemia due to medication errors associated with administration of Humalog U-200 KwikPen as communicated through the risk minimization measures.

Specifically, this protocol refers to the surveys that are designed to assess the effectiveness of communications to HCPs and patients by assessing their understanding of the risks and safe use of Humalog U-200 KwikPen which were communicated through risk minimization measures including the following key safety messages:

HCPs:

- It is not necessary to adjust the insulin dose when switching from one strength of Humalog to the other
- Humalog U-200 KwikPen should not be transferred from the KwikPen to a syringe or insulin pump
- It is necessary to specify the Humalog strength on prescriptions
- It is necessary that patients always have a backup pen

Patients:

- It is not necessary to adjust the insulin dose when switching from one strength of Humalog to the other
- Humalog 200 units/mL should not be transferred from the KwikPen to a syringe as this could result in SEVERE OVERDOSE
- It is always necessary to carry a backup pen

The surveys are also designed to answer the following process research questions to assess the effectiveness of communications to HCPs and patients through the risk minimization measures. By testing a representative population about their knowledge and understanding of key safety message themes, we can generalize the:

HCPs:

- Extent of understanding of the key safety messages for Humalog U-200 KwikPen, as communicated through the DHPC (Were the key safety messages communicated in the DHPC understood by the HCP?)

- Extent of discussion between HCPs and patients when initially prescribing or dispensing Humalog U-200 KwikPen (Did the HCP convey the key safety messages in the label and DHPC to patients when they received their initial prescription of Humalog U-200 KwikPen?) with reference to the key safety messages.

Patients:

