5.3. Study Endpoints

The additional Risk Minimization Measures will be considered effective if the majority of respondents demonstrate they are aware of the key safety messages communicated.

HCPs:

- Demonstrating that they understand the key safety messages communicated in the DHPC.
- Reporting they discuss the safe use of the product as defined in the product label and DHPC to their patients who are receiving their first prescription of Humalog U-200 KwikPen.

Patients:

- Demonstrating that they understand the key safety messages communicated about Humalog U-200 KwikPen.
- Reporting that they follow the key safety messages during administration of Humalog U-200 KwikPen.

All statistical analyses will be descriptive, i.e., no formal hypothesis will be tested.

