[BEGIN PREAMBLE 2 – DISPLAY ON SAME PAGE AS NEXT QUESTION]

The following questions are about Humalog® U-200 KwikPen®.

[END PREAMBLE 2]

15. Please answer True, False, or I don't know for each of the following statements regarding Humalog® U-200 KwikPen®.

	[RANDOMIZE LIST]	True	False	I don't know
A	Humalog® U-200 KwikPen® is approved for transfer to syringe or pump.			
B	The dose of insulin does not need to be converted when changing patients from one Humalog strength to the other (for example, changing a patient from Humalog U-100 units/mL to Humalog® U-200 KwikPen®).			
C	When prescribing Humalog® U-200 KwikPen®, it is important to clearly indicate the correct strength on the prescription.			
D	It is important to instruct your patients that they should always have a backup pen available.			

16. Are you aware of the Direct Healthcare Professional Communication provided to you by Eli Lilly and Company on the correct use of Humalog® U-200 KwikPen® (*insulin lispro*) to minimize medication errors?

- Yes
- No **[GO TO Q18]**
- I don't know **[GO TO Q18]**

17. Did you read the Direct Healthcare Professional Communication provided to you by Eli Lilly and Company on the correct use of Humalog® U-200 KwikPen® (*insulin lispro*) to minimize medication errors?
- Yes
 - No
 - I don't know
18. Are you aware of the patient communication Patient Information Letter/*IMPORTANT SAFETY INFORMATION FOR* Humalog® U-200 KwikPen® (*insulin lispro*) that is included in patient sample packs of Humalog® KwikPen® provided by Eli Lilly and Company?
- Yes
 - No **[GO TO Q20]**
 - I don't know **[GO TO Q20]**
19. Have you read the patient communication: Patient Information Letter/*IMPORTANT SAFETY INFORMATION FOR* Humalog® U-200 KwikPen® (*insulin lispro*) provided by Eli Lilly and Company?
- Yes
 - No
 - I don't know

[DO NOT DISPLAY QUESTION 20 IF 0 IS SELECTED IN QUESTION 11]

20. Do you or another healthcare professional at your practice discuss the safe use of the Humalog® U-200 KwikPen® to patients receiving their initial prescription?
- Yes
 - No
 - I don't know

[DO NOT DISPLAY QUESTION 21 IF 0 IS SELECTED IN QUESTION 11]

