	[RANDOMIZE LIST]	True	False	I don't know
A	Humalog® U-200 KwikPen® should only be injected using the prefilled KwikPen device in which it is supplied.			
B	Your dose of insulin does not need to be converted when changing from one strength of Humalog to the other (for example, changing from Humalog U-100 KwikPen to Humalog® U-200 KwikPen®).			

16. Please answer Yes, No, or I don't know for each of the following statements about the Patient Information Letter/*IMPORTANT SAFETY INFORMATION FOR* Humalog® KwikPen®, 200 units/mL, U-200 *insulin lispro* injection.

[RANDOMIZE LIST]		Yes	No	I don't know
A	The first time I was prescribed Humalog® U-200 KwikPen®, my doctor or nurse provided me with a paper copy of the Patient Information Letter/ IMPORTANT SAFETY INFORMATION . (This letter was included with the patient sample pen pack.)			
B	My doctor or nurse offered to explain information about the safe use of Humalog® U-200 KwikPen® the first time I was prescribed this product.			
C	I think about the important safety information for Humalog® U-200 KwikPen® to remind myself of the risks when injecting my insulin.			
D	I should always have a backup pen with me.			
E	It is ok to transfer insulin from the pen using a syringe.			

17. Other than the information you have received from your doctor or nurse, from what sources have you received and/or accessed information on the safe use and understanding of the Humalog® U-200 KwikPen®. (Please select all that apply.)

[RANDOMIZE LIST – KEEP OTHER AT THE BOTTOM]

- Pharmacist
- Other Healthcare Professional
- Diabetes Support Group
- Internet
- Product Warning Label
- Other

[TELEPHONE: BEGIN SAFETY EVENT/PRODUCT COMPLAINT – KEEP ON ONE PAGE]

(INTERVIEWER: Please record if respondent spontaneously reported a safety event or product complaint during the course of this interview.)

- Yes
- No **[GO TO CLOSING 1]**

Enter Safety Event or Product Complaint Verbatim

[MULTILINE INPUT]

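### The patient survey has no item on whether patients follow the key safety messages, so the patient behaviour endpoint in Section 5.3 is not measured

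*Protocol*

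**What the plan says.** Section 4 sets two objectives. The primary concerns "HCP and patient understanding regarding the risk of hypoglycemia and/or hyperglycemia due to medication errors". The other is stated as follows: "The secondary objective is to evaluate behavior of HCPs and patients regarding the risk of hypoglycemia and/or hyperglycemia". Section 4 then makes understanding concrete through messages "which were communicated through risk minimization measures including the following key safety messages": four for HCPs and three for patients. The second patient message carries a consequence: "Humalog 200 units/mL should not be transferred from the KwikPen to a syringe as this could result in SEVERE OVERDOSE".

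Section 5.3 gives patients two endpoints, understanding and behaviour. The behaviour endpoint is "Reporting that they follow the key safety messages during administration of Humalog U-200 KwikPen". Section 5.6 lists patient behaviour among the data to be collected, and Section 5.9 lists patients' self-reported practices among the outputs. Section 4 puts the matching process question in terms of consideration of the messages during administration, and explains it in parentheses as whether the patient will follow them. Section 5.5 speaks of potential behaviour.

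The candidate patient items are Q15A–B and Q16A–E in Appendix I.3. They include "I should always have a backup pen with me" (Q16D) and "It is ok to transfer insulin from the pen using a syringe" (Q16E). For HCPs, Q20 in Appendix I.1 asks: "Do you or another healthcare professional at your practice discuss the safe use of the Humalog® U-200 KwikPen® to patients receiving their initial prescription". Q21 asks the same about the patient letter.

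**The concern.** An endpoint about reported conduct needs at least one item in which the respondent reports conduct, or at least intended conduct. The patient items appear to ask what is right, what was received and what the patient thinks about. If so, the report could state that most patients follow the messages on the strength of answers that show only that they know them.

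The distinction matters for this product. Section 3.1 justifies the additional measures by human factors findings that some patients may draw insulin out with a syringe when the device malfunctions, despite the warnings on the pen and in the instructions. The worry is conduct in spite of information, and knowledge scores cannot stand in for that. The questionnaire is fixed in the appendix, so no later analysis can recover data that were never collected.

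**Working it through.** This is a question of content, so the check is an item-by-item mapping.

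**Patient survey (Appendix I.3), seven statements**

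| Item | What it asks | Type |
|---|---|---|
| Q15A | Inject only with the supplied device (True/False) | Knowledge |
| Q15B | No dose conversion between strengths (True/False) | Knowledge |
| Q16A | Paper letter received at first prescription | Receipt |
| Q16B | Doctor or nurse offered an explanation | Receipt |
| Q16C | Thinks about the safety information when injecting | Consideration |
| Q16D | Should have a backup pen | Knowledge (normative wording) |
| Q16E | Acceptable to transfer with a syringe | Knowledge (acceptability wording) |

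Q17 asks about information sources and is not a candidate.

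**Messages against items**

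| Patient message (Section 4) | Knowledge item | Practice or intention item |
|---|---|---|
| No dose adjustment on switching strength | Q15B | none |
| No transfer to a syringe | Q15A, Q16E | none |
| Carry a backup pen | Q16D | none |

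All 3 of 3 instructed actions have a knowledge item; 0 of 3 have an item on what the patient does or would do.

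**Q16C as the remaining candidate.** It names no message, so a Yes cannot be tied to any of the three. It records a thought, not an act. Q8 does not terminate respondents who say they have not used the pen yet, so some people may answer about injecting a product they have never injected. The correct-answer document scores Yes as correct, which treats the item as something to get right rather than a report of practice.

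**Consequence element.** Patient items that mention overdose, hypoglycemia or hyperglycemia: 0 of 7. The clause on severe overdose in the second patient message is therefore untested. The HCP knowledge items (Q15A–D) do not mention these outcomes either, but none of the four HCP messages listed in Section 4 does, so for HCPs there is no mismatch between messages and items.

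**HCP discussion.** Section 5.3 words the HCP endpoint as discussing the safe use of the product, and Q20 nearly repeats it. One difference remains: the endpoint is about the respondent, while Q20 and Q21 also count another professional at the same practice.

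**Sample size.** Equation 1 in Section 5.7 reproduces Table 1. At 80%, 1.96 × √(0.80 × 0.20 / 280) = 0.0469, or 4.7 points; at 50%, 1.96 × √(0.50 × 0.50 / 280) = 0.0586, or 5.9 points. Both match. The table is sound, but a narrow interval around a knowledge item remains an interval for knowledge.

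**The case against.** The best defence is that the protocol itself works with a softer construct. Section 4 speaks of consideration during administration, Section 5.5 of potential behaviour, and Q16C fits the first of these closely. This stands to the extent that Q16C does answer the consideration question. It does not rescue the endpoint, because Section 4 explains consideration as following, Section 5.3 says follow, Section 5.9 promises practices, and Q16C shows none of these.

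A second defence is that Section 5.11 already concedes that reported practices may differ from actual ones. That limitation presupposes that practices are reported, and for patients they are not.

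A third is that Section 7 says the Internet survey has no questions that could identify a safety event, a term defined there to include misuse and medication error. This is a real constraint on asking about past syringe transfer. It does not rule out asking about carrying a backup pen, and a hypothetical question can be checked against it.

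Three stronger readings are tempting and should be resisted:

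- A reader might infer that the surveys cannot answer the secondary objective at all. The HCP half is measured by Q20 and Q21.
- A reader might infer that the primary objective is untested because no item names hypoglycemia or hyperglycemia. Section 4 defines understanding through the key messages, and every instructed action has an item (4 of 4 for HCPs, 3 of 3 for patients).
- A reader might infer that the HCP discussion rate is inflated by a known amount. The documents give nothing from which to estimate the share of Yes answers that reflect only a colleague.

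**Conclusion.** The point holds for the patient half of the secondary objective. No item records what a patient does or would do on any of the three messages, so the study cannot support a statement that a majority follow them. This rests on reading the wording of Q16D and Q16E as knowledge and Q16C as thinking. It needs no numerical assumption.

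Two lesser points go with it: one clause of one patient message (the overdose consequence) is untested, and the HCP discussion rate is a practice-level figure.

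This should be fixed but is not fatal. The analyses are descriptive, the understanding endpoints are covered apart from that clause, the sample size is unaffected, and rewording alone would make the claims match the data.

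**What to change.** Before launch:

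1. Add one patient practice item on whether the respondent carries a backup pen, and one hypothetical intended-action item on what the respondent would do if the pen malfunctioned. Check both against the Section 7 statement on safety events, and amend either the item or that statement if they conflict.
2. Add one patient True/False/I don't know item on the overdose consequence.
3. Report Q20 and Q21 explicitly as practice-level rates, or ask separately about the respondent and about colleagues.
4. Report Q16C as consideration only, with respondents who have not yet used the pen shown separately.

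If items cannot be added, restate the patient endpoint in Sections 5.3 and 5.9 as knowledge and consideration of the key messages, and make no claim that patients follow them.

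The first route costs three short patient questions (more if Q20 and Q21 are split), reprogramming and an IRB amendment. The protocol is dated 20 May 2016 and data collection was estimated to start in August 2016, so the plan left time for this. The fallback adds no questions: it changes only protocol text, but gives up the patient behaviour result.

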5.4. Setting

The assessment surveys will be executed and the analysis will be completed within 18 months from product launch.

HCPs:

Eligible HCPs will receive an invitation letter ([APPENDIX I.2](#)) via email if an email address is available, or a letter via the United States Postal Service (USPS). The invitation letter will include: an overview of the rationale for the survey, information on how to access the survey online and by telephone, and a unique User Identification to ensure that the invitation is used only once. For telephone interviews, a trained interviewer, working from a computer-assisted telephone interviewing (CATI) script, will read questions or statements to the HCP. The letter will also contain a unique code that the respondent must provide when accessing the survey via the Internet or telephone. For telephone interviews, a trained interviewer, working from a computer-CATI script, will read questions or statements to the HCP. The average survey is expected to take approximately 15 minutes to complete.

A random sample of HCPs will be recruited to participate in the survey based on the list of HCPs to whom Lilly has provided a DHPC letter. The recruitment letter will indicate that participants will be compensated \$100 for their time and effort in completing the survey with the exception of HCPs who are licensed and practice in Minnesota, Vermont, Massachusetts or the District of Columbia in accordance with state laws. HCPs from these states can elect to participate however they will not be paid. Respondent-identifying information will be collected for the purposes of providing payment.

The response rate will be monitored throughout the data collection period. Reminder notices will be sent via email and or via the USPS. Additional recruitment methods may be explored during survey execution if necessary to achieve a total of 280 completed surveys.

Patients:

Eligible patients will receive an invitation letter ([APPENDIX I.4](#)) mailed by the PBM directly to the patient via the USPS. The invitation letter will indicate that participants will be compensated \$20 for their time and effort in completing the survey and will also include an overview of the rationale for the survey, information on how to access the survey online and by telephone, and a unique User Identification to ensure that the invitation is used only once. For telephone interviews, a trained interviewer, working from a CATI script, will read questions or statements to the patient. The letter will also contain a unique code that the respondent must provide when accessing the survey via the Internet or telephone. The average survey is expected to take approximately 15 minutes to complete.

The response rate will be monitored throughout the data collection period. If necessary, reminder notices will be sent to patients who have been invited to participate but have not responded. Additional recruitment methods may be explored prior to and or during survey launch if necessary to achieve a total of 280 completed surveys.

5.4.1. Inclusion criteria

HCPs must meet the following criteria to be eligible for inclusion in the survey:

- HCPs are aware of the insulin product Humalog U-200 KwikPen; and
- HCPs are involved in the treatment and management of patients with diabetes.

Patients must meet all of the following criteria to be eligible for inclusion in the survey:

- Patients are 18 years or older;
- Patients have diabetes; and
- Patients have filled at least one (1) prescription of Humalog U-200 KwikPen within the past 90 days.

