5.6. Data sources

In this survey, the data source for HCPs will be Lilly's list of HCPs who received the DHPC. From this data source HCPs will be invited to participate in the survey. The data source for patients will be the PBM's prescription data identifying those patients who have filled/refilled a prescription of Humalog U-200 KwikPen within 90 days prior to survey launch.

Structured questionnaires ([APPENDIX I.1](#) and [APPENDIX I.3](#)) comprised of closed-ended questions or statements with multiple response choices (i.e., questions or statements asking the respondents to choose from a defined list of responses) will be used to collect the survey data. The surveys will collect data on respondent characteristics and their responses to the risk understanding questions. The data collected from the surveys will be used to inform the evaluation of the effectiveness of the risk minimization measures.

Each survey will begin with a screening module with questions to confirm eligibility. Depending on the answers to the screening questions, survey participation will either be terminated or continued. If ineligible, the respondent is immediately notified with a "thank you" message that survey participation has ended. If eligible, the respondent is allowed to continue survey participation.

HCPs:

Screening questions:

- Agreement to participate
- Involved in the management of patients with diabetes
- Employment by Lilly, UBC, or the FDA
- Awareness of Humalog U-200 KwikPen

Data on demographic characteristics:

- Age
- Gender
- Role at facility
- Facility type
- State of practice

- HCP medical specialty (e.g., endocrinology, primary care)
- Number of years practicing medicine/nursing
- Number of Humalog U-200 KwikPen-treated patients the HCPs prescribed to or managed in the 12 month period preceding the survey (self-reported)

Data pertaining to evaluation of the effectiveness of the risk minimization measures:

The survey includes questions/statements that will assess the understanding or the risks and associated behavior of the HCPs to minimize these risks. The understanding level and behaviors will be analyzed using descriptive statistics and confidence intervals (CIs) and will be used to determine the effectiveness of the risk minimization measures:

- Awareness of the DHPC on the correct use of Humalog U-200 KwikPen
- Understanding of the key safety messages

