[DROP DOWN LIST INPUT WITH STATES TABLE, EXCLUDE PREFER NOT TO ANSWER]

[IF RESPONDENT ANSWERS MASSACHUSETTS, MINNESOTA, VERMONT, OR DISTRICT OF COLUMBIA, DISPLAY REMINDER MESSAGE 1 ON SAME PAGE AND GO TO Q4.]

[REMINDER MESSAGE 1]: If you practice and you are licensed in the District of Columbia, Massachusetts, Minnesota, or Vermont just a reminder that we appreciate your participation; however, no compensation for your services will be provided in accordance with local laws.

4. Please choose an option about your participation in this survey.
 - i. ○ I will participate in the survey and provide my contact information.
 - ii. ○ I will participate in the survey but choose not to be paid.

5. Are you involved in the management of patients with diabetes? This includes prescribing medications to treat diabetes or providing education to help manage diabetes.
- Yes
 - No **[GO TO Q7, TERMINATE AFTER Q14]**
6. What is your role in the management of patients with diabetes?
- Physician
 - Nurse Practitioner
 - Physician Assistant
 - Registered Nurse **[GO TO Q8]**
 - Other **[GO TO Q8]**
7. What is your primary medical specialty?
- General Internal Medicine
 - Endocrinology/Diabetology
 - Family Medicine
 - Other
8. How many years have you been in practice as a physician, physician assistant, or nurse since completing your medical/nursing education?
- Less than 5 years
 - 5 – 10 years
 - 11 – 15 years
 - More than 15 years

9. In what type of facility do you work?
- General Practice
 - Hospital
 - Other
10. Are you aware of the insulin product Humalog® U-200 KwikPen®?
- Yes
 - No **[GO TO Q12, TERMINATE AFTER Q14]**
 - I don't know **[GO TO Q12, TERMINATE AFTER Q14]**
11. For how many patients have you prescribed, or managed their treatment with, Humalog® U-200 KwikPen®?
- 0 **[TERMINATE AFTER QUESTION 14 IF 140 OR MORE COMPLETE RESPONDENTS HAVE ANSWERED 0, WHERE 140 IS A CONFIGURABLE NUMBER]**
 - 1 – 5
 - 6 – 10
 - 11 – 20
 - More than 20

12. Have you or any of your immediate family members ever worked for Eli Lilly and Company (Lilly), United BioSource Corporation (UBC), or the Food and Drug Administration (FDA)?

- Yes **[TERMINATE AFTER QUESTION 14]**
- No
- I don't know **[TERMINATE AFTER QUESTION 14]**

13. Which of the following groups best describes your age?

- Less than 30
- 30 – 39
- 40 – 49
- 50 – 59
- 60 – 69
- 70 or older

14. What is your gender?

- Male
- Female

[END SCREENING QUESTIONS]

[BEGIN SURVEY CONTENT]

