 - More than 15 years
 - I don't know

5. Do you use injectable insulin to treat your diabetes?
- Yes
 - No **[GO TO Q10, TERMINATE AFTER Q14]**
 - I don't know **[GO TO Q10, TERMINATE AFTER Q14]**
 - I don't have diabetes **[GO TO Q10, TERMINATE AFTER Q14]**
6. For how long have you been using injectable insulin to manage your diabetes?
- Less than 1 year
 - 1 – 5 years
 - 6 – 10 years
 - 11 – 15 years
 - More than 15 years
 - I don't know **[GO TO Q10, TERMINATE AFTER Q14]**
7. Have you been prescribed Humalog® U-200 KwikPen® at least once?
- Yes
 - No **[GO TO Q10, TERMINATE AFTER Q14]**
 - I don't know **[GO TO Q10, TERMINATE AFTER Q14]**
 - I don't have diabetes/I don't use insulin **[GO TO Q10, TERMINATE AFTER Q14]**

8. For how long have you been using Humalog® U-200 KwikPen®?
- I have not used the Humalog® U-200 KwikPen® yet
 - Less than 3 months
 - 3 – 6 months
 - 7 – 12 months
 - More than 1 year
 - I don't know
 - I don't have diabetes/I don't use Humalog® U-200 KwikPen® **[GO TO Q10, TERMINATE AFTER Q14]**
9. What type of mealtime insulin did you use prior to using Humalog® U-200 KwikPen®?
- Humalog® U-100 KwikPen®
 - Other 100 Units/mL insulin
 - I don't know
 - I don't have diabetes/I don't use Humalog® U-200 KwikPen® **[TERMINATE AFTER Q14]**
10. What is your gender?
- Male
 - Female

11. What is the highest level of education you have completed?

- Less than high school
- Some high school
- High school graduate/GED (General Education Diploma)
- Some college/Associate's degree
- Bachelor's degree
- Master's degree
- Professional or Doctoral degree
- Prefer not to answer

12. In what state do you live?

[DROP-DOWN LIST INPUT WITH STATES TABLE, EXCLUDE PREFER NOT TO ANSWER]

13. Which of the following groups best describes your age?

- Under 18 **[TERMINATE AFTER Q14]**
- 18 – 29
- 30 – 39
- 40 – 49
- 50 – 59
- 60 – 69
- 70 or older
- Prefer not to answer **[TERMINATE AFTER Q14]**

14. Have you or any of your immediate family members ever worked for Eli Lilly and Company (Lilly), United BioSource Corporation (UBC), or the Food and Drug Administration (FDA)?
- Yes **[TERMINATE]**
 - No
 - I don't know **[TERMINATE]**

[END SCREENING QUESTIONS]

[BEGIN SURVEY CONTENT]

[BEGIN PREAMBLE 2 – DISPLAY ON SAME PAGE AS NEXT QUESTION]

The following questions are about Humalog® U-200 KwikPen®.

[END PREAMBLE 2]

15. Please answer True, False, or I don't know for each of the following statements about Humalog® U-200 KwikPen®.

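### DHPC awareness is measured only among HCPs who already know the product, and two patient screener items end the survey for failed recall that no eligibility criterion requires

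*Protocol*

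**What the plan says.** **HCPs.** Section 5.6 sets the sampling frame: "the data source for HCPs will be Lilly's list of HCPs who received the DHPC". Section 5.4.1 then requires that "HCPs are aware of the insulin product Humalog U-200 KwikPen". In Appendix I.1, Q10 asks "Are you aware of the insulin product Humalog® U-200 KwikPen". *No* and *I don't know* are routed alike: "I don't know [GO TO Q12, TERMINATE AFTER Q14". The key-message items (Q15) and the DHPC awareness item (Q16) come after that exit. Section 5.6 lists DHPC awareness among the results used to determine whether the measures are effective.

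**Patients.** The written criterion in section 5.4.1 is "Patients have filled at least one (1) prescription of Humalog U-200 KwikPen within the past 90 days", and section 5.6 takes this from the pharmacy benefits manager (PBM) records. In Appendix I.3, Q6 asks "For how long have you been using injectable insulin to manage your diabetes" and Q7 asks "Have you been prescribed Humalog® U-200 KwikPen® at least once". *I don't know* terminates at both, and *No* also terminates at Q7. At Q4 (years with diabetes) and Q8 (time on U-200), *I don't know* continues.

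**Analysis.** Section 6.2 restricts the analysis to completed surveys. Section 5.9 promises counts of ineligible respondents with reasons, but does not say that any awareness or comprehension estimate will use them. Section 5.11 does not mention this selection.

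**The concern.** The DHPC is a letter about this product. An HCP on the mailing list who does not know that the product exists can hardly be aware of the letter. That person is the clearest case of the letter not getting through, and the screener takes that person out of the denominator. What remains is DHPC awareness given product awareness, which is not awareness among those to whom the letter was sent.

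This sits badly with the protocol's own logic. Section 5.11 treats reported non-receipt as a dissemination shortfall, and section 5.9 scores *I don't know* on a key message as incorrect. At Q10 the same answer removes the respondent instead. Lack of experience does not explain the gate, because HCPs with no U-200 patients are deliberately admitted at Q11.

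On the patient side, the fill is already documented. A patient who filled the pen but is unsure of having been prescribed that strength, or who cannot say how long insulin has been used, meets section 5.4.1 and no exclusion in section 5.4.2, yet is dropped. Such patients may well know the key messages less well than those who stay.

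**Working it through.** **1. The plan's own figures.** Equation 1 in section 5.7 at n = 280 and a rate of 60% gives 1.96 × √(0.60 × 0.40 / 280) = 5.7 points, as in Table 1. The other four rows also reproduce (5.9, 5.4, 4.7 and 3.5 points at 50%, 70%, 80% and 90%). The table is right for completers and makes no allowance for selection.

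**2. HCP DHPC awareness.** Let a be awareness among completers, u the share of otherwise eligible respondents who fail Q10, and q awareness among those who fail. Over all otherwise eligible respondents:

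rate = a(1−u) + q·u

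For awareness of a letter about an unknown product, q = 0 is the natural value. The rate is then a(1−u), and the reported figure is too high by a factor 1/(1−u). Neither a nor u is in the protocol; a = 60% and u = 10–30% are assumptions.

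| u (assumed) | Screened out per 280 completers, 280u/(1−u) | Factor 1/(1−u) | Reported 60% becomes |
|---|---|---|---|
| 10% | 31 | 1.11 | 0.60 × 0.9 = 54% |
| 20% | 70 | 1.25 | 0.60 × 0.8 = 48% |
| 30% | 120 | 1.43 | 0.60 × 0.7 = 42% |

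**3. Compared with the stated precision.** With q = 0 the bias is a·u. It equals the Table 1 half-width h when u = h/a: 9.6% at an observed 60%, 11.7% at 50% and 3.9% at 90%. A larger sample does not reduce it.

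**4. Comprehension.** The general bias is u(p−q), with p the rate among completers and q the rate among those removed. Here q = 0 is not the natural value. Some HCP items (strength on the prescription, backup pen) can be answered correctly without knowing the product. For an observed 80%:

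- q = 0: 72% at u = 10%, 64% at u = 20%.
- q = 50%: 0.9 × 80 + 0.1 × 50 = 77% at u = 10%; 0.8 × 80 + 0.2 × 50 = 74% at u = 20%.

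The bias is upward only if q is below p. For patients neither u nor q is known, so no size can be given.

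**5. Patient routing against the written criteria.**

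| Item | Answer | Routing | Required by 5.4? |
|---|---|---|---|
| Q4, years with diabetes | *I don't know* | continues | no |
| Q6, years on insulin | *I don't know* | terminates | no |
| Q7, ever prescribed U-200 | *I don't know* | terminates | no |
| Q7, ever prescribed U-200 | *No* | terminates | yes, under 5.4.2 |
| Q8, time on U-200 | *I don't know*, or not used yet | continues | no |

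A user who cannot date the start of insulin leaves, while someone who has not yet used the pen stays. Section 5.6 also lists a screening question on a fill within 90 days; no item in Appendix I.3 asks it.

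**The case against.** **The HCP population is declared.** Sections 5.2 and 5.4.1 say openly that eligible HCPs know the product, and section 5.11 limits generalisation to HCPs educated about it. That stands for comprehension: asking content questions about an unknown product is of little use, and keeping Q10 as the gate to them is reasonable. It does not rescue Q16, which concerns a letter sent to everyone on the list.

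**The counts will be reported, and an extra denominator is SAP material.** This largely stands as to remedy. HCPs who fail Q10 have already answered role, specialty and setting, and still answer the employment, age and gender items, so the wider denominator can be formed from planned data. But the routing and the completers-only rule are fixed in the protocol, and the limitation belongs in section 5.11.

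**Q7 *No* implements a written exclusion.** This stands. Section 5.4.2 excludes patients not prescribed the product, and some *No* answers may be true record mismatches. It does not cover *I don't know* at Q7, nor anything at Q6.

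**Stronger readings that the protocol does not support.** A reader might infer that an observed 60% majority is lost once u passes 1 − 0.5/0.6 = 16.7%. The majority criterion in section 5.3 concerns understanding of the key messages and the related behaviour; it sets no threshold for DHPC awareness. A reader might also infer that every awareness and comprehension rate is pushed upward, or that a(1−u) applies to patients. Both need those removed to score lower, or zero, and nothing in the protocol establishes that.

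**Conclusion.** The point holds in limited form. HCP DHPC awareness, a result that section 5.6 uses to judge effectiveness, is conditional on knowing the product and is biased upward relative to the list from which HCPs are drawn. The direction is close to certain. The size, a factor 1/(1−u), rests on q = 0 and on a u that the protocol does not give. The fall from 60% to 54–42% for u = 10–30% is illustrative and says nothing by itself about whether the measures would be declared effective.

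For patients, *I don't know* at Q6 and Q7 terminates PBM-identified fillers on grounds found in neither section 5.4.1 nor 5.4.2, and inconsistently with Q4 and Q8. Upward bias in comprehension is likely, not certain, and cannot be computed. Q6 is the lesser defect, since it tests recall of duration and not awareness of the product or its messages.

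**What to change.** 1. Keep Q10 as the gate to the content questions. Report DHPC awareness twice: among completers, and over all otherwise eligible diabetes-managing respondents from the DHPC list, counting Q10 *No* and *I don't know* as not aware. Report u. If the Q11 cap on HCPs with no U-200 patients (140, configurable) closes during fieldwork, count those it terminates separately, because they too are never asked Q16.
2. Remove the termination on Q6 *I don't know*.
3. Let Q7 *I don't know* continue for PBM-confirmed fillers. Q7 *No* may stay terminated under section 5.4.2, with its count reported.
4. If comprehension is shown with screened-out people counted as incorrect, label it a worst-case bound, since they were never asked.
5. Add this selection to section 5.11.

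The cost is two skip-logic edits, one extra denominator from screener data already collected, and a sentence or two of text. No extra recruitment is needed. The downside is that reported rates become somewhat less favourable.
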